3.4 Risk and Benefit Rationale

This study adopts a strict risk-benefit assessment system. Potential risks mainly include three aspects: rTMS-related risks (10-15% of subjects may experience transient headache or scalp discomfort, seizure risk <0.1%); pinaverium bromide may cause dry mouth and constipation (incidence about 12%); bifidobacterium may cause mild bloating (incidence 8-10%). Main benefits are reflected in: 1) Clinical level: it is expected that 60% of patients in the combination therapy group will achieve a reduction in abdominal pain VAS score of $\geq 50\%$, and an increase in quality of life score (IBS-QOL) of ≥ 20 points; 2) Long-term benefit: the recurrence rate in the combination group at the 3-month follow-up is significantly lower than in the single-drug groups.

4. Sample Size Calculation

We tested the null hypothesis of no difference in composite response rates between groups. Based on previous literature¹⁸⁻²⁰ and our preliminary trial, assuming a placebo response rate of 23.8%, we expected to double the response rate, assuming a composite response rate for repetitive transcranial magnetic stimulation of 47.61%. At a significance level of $\alpha = 0.05$, 63 patients per group are needed to detect a 23% difference with 80% statistical power. Considering a 10% dropout rate, the final estimated sample size required is 140 patients. [This center will recruit 70 cases, Xiangcheng People's Hospital of Suzhou will recruit 40 cases, and Suzhou New District People's Hospital will recruit 30 cases.

PASS 2021, v21.0.3

2025/7/20 10:54:31 1

Tests for Two Proportions

Numeric Results for Testing Two Proportions using the Z-Test with Pooled Variance
 Hypotheses: H0: P1 - P2 = 0 vs. H1: P1 - P2 ≠ 0

Target Power	Actual Power*	N1	N2	N	P1	P2	Diff D1	Alpha
0.8	0.80393	63	63	126	0.47619	0.2381	0.2381	0.05

* Power was computed using the normal approximation method.

References

 Fleiss, J. L., Levin, B., and Paik, M.C. 2003. Statistical Methods for Rates and Proportions. Third Edition. John Wiley & Sons. New York.

Dropout Rate (DR) is the percentage of subjects (or items) that are expected to be lost at random during the course of the study and for whom no response data will be collected (i.e., will be treated as "missing"). N1, N2, and N are the evaluable sample sizes at which power is computed. If N1 and N2 subjects are evaluated out of the N1' and N2' subjects that are enrolled in the study, the design will achieve the stated power. N1', N2', and N' are the number of subjects that should be enrolled in the study in order to end up with N1, N2, and N evaluable subjects, based on the assumed dropout rate. After solving for N1 and N2, N1' and N2' are calculated by inflating N1 and N2 using the formulas N1' = N1 / (1 - DR) and N2' = N2 / (1 - DR), with N1' and N2' always rounded up. (See Julius, S.A. (2010) pages 52-53, or Chow, S.C., Shao, J., Wang, H., and Lokhnygina, Y. (2018) pages 32-33.) D1, D2, and D are the expected number of dropouts. D1 = N1' - N1, D2 = N2' - N2, and D = D1 + D2.

Procedure Input Settings

Autosave Inactive

Design Tab

Solve For:	Sample Size
Power Calculation Method:	Normal Approximation
Alternative Hypothesis:	Two-Sided
Test Type:	Z-Test (Pooled)
Power:	0.80
Alpha:	0.05
Group Allocation:	Equal (N1 = N2)
Input Type:	Proportions
P1 (Group 1 Proportion H1):	0.476190476
P2 (Group 2 Proportion):	0.238095238

5. Detailed Study Content

5.1 Overall Study Design:

Project Title: The Effect of Repetitive Transcranial Magnetic Stimulation Combined with Pinaverium Bromide or Bifidobacterium versus Sham Stimulation on Chronic Visceral Pain in Patients with Diarrhea-Predominant Irritable Bowel Syndrome: A Randomized, Controlled Factorial Design Study

Study Type: Prospective 2*2 factorial designed randomized controlled study

This is a multicenter, prospective, 2*2 factorial designed randomized controlled study¹⁹ evaluating the effectiveness of TMS for treating irritable bowel syndrome. This study will recruit and screen subjects according to ethical review standards. Subjects will be randomly divided into an rTMS stimulation + pinaverium bromide treatment group, an rTMS stimulation + bifidobacterium treatment group, a pinaverium bromide + sham rTMS treatment group, and a bifidobacterium + sham rTMS stimulation group for clinical trials. Pain and stool characteristics will be assessed after 2 weeks of treatment, and data will be collected and analyzed finally. This study aims to deeply explore the clinical efficacy of Transcranial Magnetic Stimulation (TMS) on chronic visceral pain in patients with Irritable Bowel Syndrome (IBS), in order to provide more reliable and effective therapeutic targets for clinical application.

5.2 Subject Grouping

Intervention measures (Including whether the investigational drugs are used off-label. If used

off-label, the safety and necessity of the research must be justified, and the off-label use must be detailed in the informed consent form.)

(1) IBS-D patients receiving rTMS stimulation + pinaverium bromide treatment

rTMS stimulation: 1 Hz, 80% MT, 20 min/d, once daily for 2 weeks;

Pinaverium bromide: Oral, 3 times daily, 1 tablet/time, for 2 weeks;

(2) IBS-D patients receiving rTMS stimulation + bifidobacterium treatment

rTMS stimulation: 1 Hz, 80% MT, 20 min/d, once daily for 2 weeks;

Probiotic: Oral, 2 times daily, 4 capsules/time, for 2 weeks;

(3) IBS-D patients receiving Sham rTMS stimulation + pinaverium bromide treatment

Sham rTMS treatment: 0 Hz, 0% MT, 20 min/d, once daily for 2 weeks;

Pinaverium bromide: Oral, 3 times daily, 1 tablet/time, for 2 weeks;

(4) IBS-D patients receiving Sham rTMS stimulation + bifidobacterium

Sham rTMS stimulation: 0 Hz, 0% MT, 20 min/d, once daily for 2 weeks;

Probiotic: Oral, 2 times daily, 4 capsules/time, for 2 weeks;

Dose Selection/Adjustment

rTMS stimulation: 1 Hz, 80% MT, 20 min/d, once daily for 2 weeks;

Pinaverium bromide: Oral, 3 times daily, 1 tablet/time, for 2 weeks;

Probiotic: Oral, 2 times daily, 4 capsules/time, for 2 weeks;

Administration Time

This study adopts a standardized administration time scheme to ensure treatment consistency:

Pinaverium bromide (50mg) is taken orally 30 minutes before meals three times daily,

Bifidobacterium (500mg) is taken after breakfast and before bedtime, both study drugs are

dispensed with electronic medication boxes (MediSafe system) for timed reminders and

medication recording.

Blinding/Unblinding

Blinding method: rTMS real/sham stimulation uses identical equipment and operating sounds, administered by an independent technician through an encrypted control system; drugs (pinaverium bromide/bifidobacterium) use matching placebos (identical capsules, boxes, labels),

distributed uniformly by the central pharmacy according to random codes; 2) Statistical unblinding: Unblinding is performed in two stages after database lock -- first, an independent statistician performs inter-group comparisons (Group A vs. B vs. C vs. D), the final reveal of the intervention corresponding to each group occurs after the main conclusions are formed; 3) Quality control: Blinded assessment is conducted monthly, accidental unblinding events must be recorded within 48 hours and the impact on the study assessed.

Rescue Medication and Supportive Therapy (Necessary treatment measures when SAEs related to the study occur)

This study establishes strict norms for rescue medication and supportive therapy: 1) rTMS-related SAE: Seizure - immediately stop stimulation and intravenous push diazepam (5-10mg), transfer persistent convulsions to neurological ICU for monitoring; Severe headache/dizziness - administer paracetamol (≤ 1 g/dose) combined with vestibular inhibitors; 2) Drug-related SAE: Pinaverium bromide allergic reaction - immediately discontinue drug and intramuscular injection of adrenaline (0.3-0.5mg, 1:1000), oral loratadine (10mg/day); Bifidobacterium-induced bacteremia - immediately stop administration and intravenous infusion of vancomycin (15mg/kg q12h) combined with blood culture-guided treatment; 3) Psychological support: Worsening anxiety/depression (HADS score increase ≥ 8 points) - refer to psychological department for intervention. All SAE treatments are executed by the research center's 24-hour emergency team, using standardized (emergency kits) (containing the above drugs and rescue equipment), the treatment process involves continuous ECG monitoring and recording of vital sign changes. Costs of rescue medication are covered by research insurance, subsequent medical follow-up for subjects continues until symptoms completely resolve + 2 weeks. After SAE resolution, the causal relationship with the intervention measures is assessed by an independent medical committee, major SAEs (e.g., anaphylactic shock) require re-evaluation of the individual's risk-benefit ratio for continuing the study. All rescue measures are recorded in the source documents and synchronized to the eCRF system, serving as key data for safety analysis.

6. Study Implementation Procedures

Subject Management

Subject recruitment methods: Establish open and transparent channels, publish recruitment information approved by the Ethics Committee, post recruitment advertisements, etc., so that patients with potential enrollment opportunities can directly contact the researchers.

Informed consent process: Include privacy protection in the informed consent form, fully inform the subjects, obtain their consent, so that subjects know their personal information and privacy are protected by law and the research team will use it reasonably according to legal provisions and the requirements of documents such as the informed consent form. Once it is found that the subject's personal information or privacy is violated, the subject can raise questions or even resort to legal means, and these actions will not affect normal clinical diagnosis and treatment.

Screening number allocation

Take confidentiality measures to ensure the confidentiality of research project materials, such as using codes to mark subject identification information. The subject's name and other identifying information should be replaced with a "subject identification code" to ensure that identity information, disease information, biological sample information, and other data are provided to other trial researchers after encoding processing; use subject identification codes on case report forms;

Post-treatment visits (Safety follow-up visits, follow-up visits, survival follow-up)

This study designs a comprehensive post-treatment follow-up system to ensure long-term efficacy and safety assessment: a 12-week follow-up period is conducted after the last treatment.

7. Research Data Management and Statistical Analysis.

This study adopts strict data management and statistical analysis methods to ensure the scientificity and reliability of the randomized controlled factorial design study.

8. References

1. Chey WD, Kurlander J and Eswaran S. Irritable bowel syndrome: a clinical review. *Jama* 2015; 313: 949-958. 2015/03/04. DOI: 10.1001/jama.2015.0954.
2. Camilleri M. Diagnosis and Treatment of Irritable Bowel Syndrome: A Review. *Jama* 2021; 325: 865-877. 2021/03/03. DOI: 10.1001/jama.2020.22532.

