Study Protocol

(Version number: 2.0 Version date: 2025.08.21)

Project Title: Effect of Transcranial Magnetic Stimulation vs Sham Stimulation Combined With Pinaverium Bromide vs Bifidobacteria in Diarrhea-Predominant Irritable Bowel Syndrome: A 2×2 Factorial Randomized Clinical Trial

Sponsor: The First Affiliated Hospital of Soochow University

Responsible Department: Gastroenterology Department

Principal Investigator: [name]

Participating Centers: Xiangcheng People's Hospital of Suzhou, The People's Hospital of Suzhou New District

Investigator Statement and Protocol Signature Page

As the principal investigator of this research project, I hereby commit to adhering to the ethical principles outlined in the National Health Commission's "Ethical Review Measures for Biomedical Research Involving Humans" (2016), the WMA's "Declaration of Helsinki" (2013), the CIOMS's "International Ethical Guidelines for Biomedical Research Involving Human Subjects" (2002), and Good Clinical Practice (GCP). Under the guidance of the Quality Management Standards for Drug Clinical Trials, I will implement the study protocol approved by the Ethics Committee and conduct the research in strict accordance with the requirements of this protocol, ensuring the scientific validity of the study and protecting the health and rights of the subjects.

Name: [name]

Signature:

Date:2025.07.01

Protocol Synopsis

Study objective	(1) To evaluate the alleviating effect of repetitive transcranial magnetic stimulation (rTMS) on chronic visceral pain in patients with diarrhea-predominant irritable bowel syndrome (IBS-D); (2) To assess the interventional effect of pinaverium bromide and bifidobacterium used alone on chronic visceral pain in IBS-D; (3) To analyze potential interactions between the two intervention measures.
Sample size	140
Study population	Patients with diarrhea-predominant irritable bowel syndrome
Study design	Randomized, controlled factorial design study
Inclusion criteria	(1) Age range 18-75 years (either sex) (2) Fulfilling the Rome IV criteria for irritable bowel syndrome diagnosis (3) Bristol stool type 6-7 in >25% and type 1-2 in <25% of bowel movements (4) Patients experienced Bristol stool type 6 or 7 on ≥ 4 days with mean abdominal pain score ≥ 3 during the initial 2-week period

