Exclusion criteria	(1) Documented organic gastrointestinal pathology; endocrinologic or metabolic diseases with known gastrointestinal motility effects including diabetes mellitus and hyperthyroidism; previous surgical interventions involving abdominal cavity intestinal tract or anal region (2) current use of any medication with documented effects on gastrointestinal motility or secretory function; administration of concurrent therapies or pharmacologic agents capable of confounding treatment efficacy or safety evaluations (3) pregnancy lactation or postpartum status within 12

	
months
 
(4) noncompliance with randomized treatment allocation or demonstrated poor adherence tendencies

Intervention	
(1) IBS patients receiving rTMS stimulation + pinaverium bromide treatment
 
rTMS stimulation: 1 Hz, 80% MT, 20 min/d, once daily for 2 weeks;
 
Pinaverium bromide: Oral, 3 times daily, 1 tablet/time, for 2 weeks;
 
(2) IBS patients receiving rTMS stimulation + bifidobacterium treatment
 
rTMS stimulation: 1 Hz, 80% MT, 20 min/d, once daily for 2 weeks;
 
Bifidobacterium: Oral, 2 times daily, 4 capsules/time, for 2 weeks;
 
(3) IBS patients receiving sham rTMS + pinaverium bromide treatment
 
Sham rTMS treatment: 0 Hz, 0% MT, 20 min/d, once daily for 2 weeks;
 
Pinaverium bromide: Oral, 3 times daily, 1 tablet/time, for 2 weeks;
 
(4) IBS patients receiving sham rTMS + bifidobacterium treatment
 
Sham rTMS stimulation: 0 Hz, 0% MT, 20 min/d, once daily for 2 weeks;
 
Bifidobacterium: Oral, 2 times daily, 4 capsules/time, for 2 weeks;

Primary endpoint	The primary outcome measure is the proportion of patients achieving a composite response at the end of treatment

	(Week 2), defined as: a reduction of $\geq 30\%$ from baseline in the average daily worst abdominal pain score, and a reduction of $\geq 50\%$ in the number of days with at least one stool consistency meeting BSFS type 6 or 7 criteria during Week 2. Abdominal pain intensity is assessed using an 11-point NRS scale (0-10) for the last 24 hours daily. Stool consistency is recorded daily by the patient selecting the most representative category according to the BSFS.

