Secondary endpoints	
1) Anorectal manometry: Record the subject's initial sensation threshold, constant urge sensation threshold, and maximum tolerable volume at baseline (before treatment) and after the end of treatment.
 
2) IBS Symptom Severity Score (IBS-SSS): Evaluated at 1 week, 2 weeks, and 4 weeks after treatment.
 
3) IBS Quality of Life (IBS-QoL) score: Evaluated at 1 week, 2 weeks, and 4 weeks after treatment.

Study timeline	2025.07.1-2026.03.30: Recruit 20-25 patients with diarrhea-predominant IBS meeting Rome IV criteria monthly through multiple centers, using standardized screening procedures (including symptom assessment, exclusion checks, and baseline tests), aiming to complete randomization of 140 cases within 12 months.
Statistical analysis	Use Shapiro-Wilk test to assess normality. Parametric t-test, Wilcoxon rank-sum test, or Kruskal-Wallis test will be used to evaluate continuous data between groups as appropriate.

1. Background

Irritable bowel syndrome (IBS) is a clinically common functional gastrointestinal disorder, affecting 10%-25% of the world's population. The prevalence of IBS in China ranges from 5% to 11%¹. Among patients visiting the gastroenterology specialty outpatient clinic of our hospital, IBS accounts for more than one-third of cases, with diarrhea-predominant IBS (IBS-D) being the most common subtype. Current symptomatic treatments in both Western and traditional Chinese medicine can temporarily alleviate symptoms of intestinal dysmotility. However, these therapies may cause varying degrees of side effects and lack personalized treatment strategies. In Western countries, over 50% of patients turn to complementary and alternative therapies due to insufficient or unstable symptom relief following pharmacological treatment².

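### The exclusion list does not bar patients with known hypersensitivity to pinaverium bromide, although the protocol's own rescue plan foresees an allergic reaction to it (low severity, safety only)

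*Protocol*

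**What the plan says.** The Synopsis gives four inclusion and four exclusion criteria.

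- **Inclusion:** age 18 to 75; the diagnosis ("Fulfilling the Rome IV criteria for irritable bowel syndrome diagnosis"); the stool-form proportions; and loose-stool days and mean pain over the initial two weeks.
- **Exclusion 1:** organic gastrointestinal disease, endocrine or metabolic disease affecting motility, and previous abdominal, intestinal or anal surgery.
- **Exclusion 2:** "current use of any medication with documented effects on gastrointestinal motility or secretory function", together with "administration of concurrent therapies or pharmacologic agents capable of confounding treatment efficacy or safety evaluations".
- **Exclusion 3:** pregnancy, lactation and the postpartum period.
- **Exclusion 4:** "noncompliance with randomized treatment allocation or demonstrated poor adherence tendencies".

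Section 3.2 (Subject Selection Rationale) repeats inclusion items only. The Study timeline row of the Synopsis mentions screening that covers symptoms, exclusion checks and baseline tests, without further definition.

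Section 5.2, under rescue medication, lists among drug-related serious adverse events: "Pinaverium bromide allergic reaction - immediately discontinue drug and intramuscular injection of adrenaline", at 0.3 to 0.5 mg, followed by oral loratadine. It adds that "major SAEs (e.g., anaphylactic shock) require re-evaluation" of whether the patient should continue.

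**The concern.** A documented reaction to a drug can be found by asking before randomisation. The rescue plan works only after exposure. The protocol regards a pinaverium reaction as something that may need adrenaline, yet it does not use the step that would keep patients already known to react away from the drug.

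Blinding adds to this. Section 5.2 describes matching placebos in identical presentation, distributed by a central pharmacy according to random codes. Site staff are therefore not meant to know who has been assigned pinaverium, and dispensing is not a dependable second check. Three centres also recruit to separate targets (section 4), so a shared written rule is safer than relying on each centre's judgement.

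What is at stake is an avoidable re-exposure of an individual patient. It is not the validity of the trial's result.

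**Working it through.** **1. The plan's own figures, for background.** Inputs from section 4: response rates 0.476190476 and 0.238095238, two-sided alpha 0.05, target power 80%, pooled Z-test, 10% dropout. Recomputed: 63 per group, power 0.8039 (stated 0.80393), and 126 / (1 − 0.10) = 140. These reproduce. Eligibility wording does not enter the calculation, so the point changes none of them.

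**2. Does any criterion catch a past pinaverium reaction?**

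| Text | Subject | Covers a past reaction? |
|---|---|---|
| Inclusion 1–4 | Age, diagnosis, stool form, symptom level | No |
| Exclusion 1 | Disease and surgery | No |
| Exclusion 2 | Medication or therapy in use | No: an allergy history is not a treatment being taken |
| Exclusion 3 | Pregnancy, lactation, postpartum | No |
| Exclusion 4 | Adherence | No: it concerns behaviour, not tolerance |
| Section 3.2 | Inclusion items repeated | No |
| Exclusion checks at screening | Application of the written list | No: they can only check what is listed |

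**3. Who could receive pinaverium?** Section 5.1 names four arms, two of which contain pinaverium. A patient with a documented reaction, once enrolled, could be assigned to either.

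**4. How often?** Section 3.4 gives an incidence of about 12% for dry mouth and constipation with pinaverium, and no figure for allergy. No other section gives one. An expected number of patients or events cannot be derived.

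**5. Can recruitment absorb the change?** The Study timeline says: "Recruit 20-25 patients with diarrhea-predominant IBS meeting Rome IV criteria monthly through multiple centers". The same row gives dates spanning 9 months and also speaks of completing randomisation within 12 months, so both are shown.

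| | 9 months | 12 months |
|---|---|---|
| Recruited at 20 to 25 a month | 180 to 225 | 240 to 300 |
| Margin over 140 | 40 to 85 | 100 to 160 |
| Share of margin used by 5 extra screen failures | 5/85 = 5.9% to 5/40 = 12.5% | 5/160 = 3.1% to 5/100 = 5.0% |

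The five failures are purely illustrative. If the monthly rate already counts only patients who passed the exclusion checks, which the text does not say, five would take 5/25 = 0.20 to 5/20 = 0.25 month to replace.

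**The case against.** **The rescue plan is correct and contradicts nothing.** This stands. First reactions occur in patients with no history, and they need a plan whatever the eligibility rules. A reader might infer that section 5.2 conflicts with the exclusion list; it does not. It is cited only because it shows how seriously the protocol takes the reaction. The defect lies in the list.

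**No investigator would knowingly randomise such a patient.** Probably so: the investigator statement commits to good clinical practice and to protecting subjects' health. Consent material is not part of the public text, so any allergy question asked there cannot be seen. This lowers the practical risk, but neither replaces a written criterion.

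**The point is a preference, not an error.** This is arguable, since nothing is contradicted. However, eligibility is fixed in the protocol and is not normally left to a statistical analysis plan, and the list as fixed admits a patient whom it should not. That is enough for a cheap improvement, though not for more.

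**The same should apply to bifidobacterium.** A reader might infer this, but section 5.2 foresees bacteremia for that product, not allergy. The document text supports only the pinaverium part.

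**Conclusion.** The point holds as a low-severity matter of patient safety. The only exclusion list in the protocol does not cover known hypersensitivity to pinaverium, and nothing else in the document fills the gap. Power, the total of 140 and the treatment estimate are untouched.

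No size of risk is claimed. A reader might infer a 1 in 2 danger, because 2 of 4 arms contain pinaverium and 2/4 = 0.5, or 70 of 140 patients. The documents do not support that as a measure of risk in this trial. It applies only to a patient with a documented reaction who has been enrolled, an event of unknown frequency. It also assumes equal allocation to four arms, whereas section 4 states equality only for the two groups of the power calculation.

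The conclusion rests on reading the criteria literally and on the Synopsis being the protocol's complete exclusion list.

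**What to change.** Add one exclusion criterion to the Synopsis: *known hypersensitivity to pinaverium bromide or its excipients*. Check it by history at the existing screening, before randomisation. Extending the wording to the bifidobacterium product is optional.

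No new visit or test is needed, and the sample size stays at 140. The change does require an amendment approved by the Ethics Committee. Version 2.0 is dated 2025.08.21, after the planned recruitment start of 2025.07.1, so the amendment would fall within the recruitment period. There may be a few additional screen failures, which the planned recruitment rate should absorb.
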